Modified Reporting of Positive Urine Cultures Collected from Long Term Care, a Randomized
Controlled Trial Protocol
[name], [name], [name]

Administrative Information

Protocol Version: 1.0 May 2018

Registration: www.clinicaltrials.gov identifier pending

Funding: none

Roles and responsibilities:

Protocol: [name], Associate Professor, Memorial University

Sponsor: Memorial University of Newfoundland, St. John's, NL, Canada

Role of sponsor in design, collection, management, analysis, interpretation, writing, decision to
publish: none

Principal Investigator: [name]

Co-Investigators: [name], [name]

Introduction

Background and rationale

Asymptomatic bacteriuria (ASB) is a condition in which bacteria from the bowel are detected in significant numbers by culture in a specimen of collected urine, but the patient does not have genitourinary symptoms or signs.(1) In contrast, urinary tract infection (UTI) is the presence of bacteria in urine specimens with defined symptoms or signs.(2, 3) Catheter-associated urinary tract infection (CA-UTI) is defined as presence of bacteria in urine specimens with defined symptoms or signs in the presence of an indwelling urinary catheter, and catheter-associated asymptomatic bacteriuria (CA-ASB) is defined as presence of bacteria in urine

specimens without defined symptoms or signs in the presence of an indwelling urinary catheter.(2)

The use of inappropriate antibiotic treatment for ASB is a systemic antibiotic stewardship problem, causing harm due to antibiotic adverse effects, selection of bacteria toward drug resistance, and wasted cost.(4)

UTI's are among the commonest indications for antimicrobial therapy. Prevalence of ASB varies from 1-5% among healthy premenopausal women, to 25-50% among women in long term care, to 100% among patients with chronic indwelling catheters.(5) Treatment of ASB with antimicrobial therapy does not reduce incidence of symptomatic UTI, complications or death, and is associated with adverse events.(6) Among women with ASB randomized to treatment, resistance to antibiotics among isolated bacteria increased.(7) Even among pregnant women, the treatment of ASB may not provide significant benefit.(8, 9) Various interventions have been proposed to reduce antibiotic treatment for ASB. Physicians have difficulty avoiding treatment of ASB when presented with positive culture results.

Recognizing the inappropriate treatment of ASB to be a problem in acute care, a novel intervention was defined, in which identification and susceptibility results for positive urine culture results were not made available to physicians, unless the physician called the microbiology laboratory.(10) This “modified reporting” was associated with a reduction in the rate of antibiotic treatment of AB from 48% to 12% (number needed to report for benefit = 3) among non-catheterized inpatients, using historical controls.

A randomized, unblinded controlled trial was performed in acute care in St. John's, among patients without indwelling catheters, using the same intervention.(11) Results of positive urine cultures from 110 consecutive inpatients at two urban hospitals were randomised to

standard report or modified report. Specimens randomized to the modified report were reported as follows: "This POSITIVE urine culture may represent asymptomatic bacteriuria or urinary tract infection. If urinary tract infection is suspected clinically, please call the microbiology laboratory for identification and susceptibility results."

Exclusion criteria were age less than 18 years, pregnancy, presence of an indwelling urinary catheter, samples from patients already on antibiotics, neutropenia, or admission to an Intensive Care Unit. Patients were followed for seven days, and physician treatment decisions were observed. 76/110 (69%) of positive urine cultures represented ASB. The proportion of appropriate treatment (UTI treated plus ASB not treated) was higher in the modified arm than in the standard arm (44/55 (80.0%) vs 29/55 (52.7%), absolute difference=-27.3%, RR=0.42, p=0.002, Number needed to report for benefit=3.7).

There were two bacteremias in the modified report group, and one bacteremia in the standard report group, none of which were considered related to the intervention. There were two deaths in the modified report group, and one death in the standard report group, none of which were considered related to the intervention. Based on this trial, the intervention was considered safe over 7 days of followup, and effective to reduce inappropriate treatment, but further study would be required among populations excluded from the trial.

We propose to repeat the trial using an identical design and intervention, but including only urine collected from long term care facilities (LTCF). The control arm is standard of care. We hypothesize that the modified reporting intervention will also reduce treatment of ASB in the LTCF population, without causing harm.

Objectives

Research Question: Among patients with positive urine cultures collected from LTCF reported by Health Sciences microbiology laboratory, would restricted reporting, as compared to standard reporting, lead to a reduction in the rate of inappropriate antibiotic therapy without an increase in bacteremia or death over 30 days?

Trial design

Randomized controlled trial, 2 parallel groups with equal allocation, superiority analysis.

Methods: Participants, interventions, and outcomes

The proposed study is a randomized trial of two methods of laboratory reporting in which physicians are the main research participants. At the time of positive urine culture results, the specimen will be randomized in the laboratory using computer generated random numbers placed into serially numbered sealed, opaque envelopes, into two equal groups. One group will receive modified reporting, and the other group will receive standard reporting of bacterial identification and susceptibility. Physicians receiving modified reports will have the option to call the laboratory to receive complete results, or not. Complete results will be released by laboratory information system to physicians who call to request them. Physicians will be informed about the study prior to initiation, and debriefed about the study after the results have been collected.

The primary efficacy outcome is proportion of appropriate antibiotic therapy prescribed by physicians, based on published diagnostic criteria for ASB and UTI among catheterized patients. Appropriate therapy is defined as any treatment for UTI, or no treatment for ASB. Inappropriate therapy is defined as no treatment for UTI, or treatment for ASB. The primary safety outcome is rate of bacteremia and death. The study investigators will determine the

diagnosis based on a chart assessment to determine if the patient has UTI, CA-UTI, ASB or CA-ASB.

The definition of UTI in LTCF will be based on 2017 Canadian LTCF surveillance guidelines.(12) For residents without an indwelling catheter, criteria 1 and 2 must be present with no other identified source of infection, OR criteria 2 and 3.

1. At least 1 of the following sign or symptom subcriteria:

- a. Acute pain, swelling, or tenderness of the testes, epididymis, or prostate in males
- b. Fever or leukocytosis and at least 1 of the following localizing urinary tract subcriteria:
 - i. Acute dysuria
 - ii. Acute costovertebral angle pain or tenderness
 - iii. Suprapubic pain
 - iv. Gross hematuria
 - v. New or marked increase in incontinence
 - vi. New or marked increase in urgency
 - vii. New or marked increase in frequency
- c. In the absence of fever or leukocytosis, then 2 or more of the following localizing urinary tract subcriteria:
 - i. Acute dysuria
 - ii. Suprapubic pain
 - iii. Gross hematuria
 - iv. New or marked increase in incontinence
 - v. New or marked increase in urgency
 - vi. New or marked increase in frequency

2. $\geq 10^8$ cfu/L of no more than 2 species of microorganisms from a midstream urine OR $\geq 10^5$ cfu/L of any number of organisms in a specimen collected by in-and-out catheter
3. A blood culture isolate is the same as the organism isolated from the urine and there is no alternate site of infection

For residents with an indwelling catheter (urine is collected from a single catheter urine specimen or a midstream voided urine specimen from a resident whose catheter has been removed within the previous 48 hours), criteria 1 and 2 must be present with no other identified source of infection, OR criteria 2 and 3.

1. At least 1 of the following sign or symptom subcriteria:
 - a. Fever, rigors, or new-onset hypotension, with no alternate site of infection
 - b. Either acute change in mental status or acute functional decline, with no alternate diagnosis and leukocytosis
 - c. New-onset suprapubic pain or costovertebral angle pain or tenderness
 - d. Purulent discharge from around the catheter
 - e. Acute pain, swelling, or tenderness of the testes, epididymis, or prostate in males
2. Urinary catheter specimen culture with $\geq 10^8$ cfu/L of any organism(s)
3. A blood culture isolate is the same species as the organism isolated from the urine, with the same resistance pattern, and there is no alternate site of infection

Study setting

Specimens will be collected from patients admitted to one (or more?) LTCF in St. John's, Newfoundland, Canada. The metropolitan area of St. John's has a population of 219,000 people (2017). Pleasantview Towers (430 beds) provides long term residential accommodation for frail

elderly with high care needs. One centralized microbiology laboratory performs all testing for the city.

Inclusion and exclusion criteria for participants

Consecutive positive urine cultures collected from patients admitted to LTCF will be included. All methods of urine collection will be included (midstream, in-and-out catheterization, indwelling catheter). Exclusion criteria will be urine cultures not collected from LTCF patients, pregnancy, antibiotic treatment at the time of collection, and patients known to have blood neutrophils <1.0 within 7 days.

Interventions

The modified report states “This POSITIVE urine culture may represent asymptomatic bacteriuria or urinary tract infection. If urinary tract infection is suspected clinically, please call the microbiology laboratory at [name] between 0900 to 2300, or the microbiology technologist on-call at [name] at night, for identification and susceptibility results.” The standard report provides bacterial count, bacterial identification and bacterial susceptibility results.

The report is provided to the physician approximately 24 hours after receipt of the specimen, when cultures have been examined after overnight incubation. The intervention is a single report, so it is not possible to discontinue the intervention, or change allocation during the trial. There will no other influence on concomitant care or treatment.

Outcomes

Primary efficacy outcome:

Proportion of appropriate antibiotic therapy prescribed by physicians. Appropriateness is determined by investigators based on chart review, based on diagnosis of UTI or ASB. Appropriateness is determined within two days from positive urine culture.

Secondary efficacy outcomes:

Proportion of calls from physicians requesting complete report

Primary safety outcomes:

Mortality rate over thirty days from positive urine culture.

Bacteremia rate over thirty days from positive urine culture.

Adverse event rate over seven days from positive urine culture.

Participant timeline

TIMEPOINT	STUDY PERIOD				
	Enrolment	Allocation	Post-allocation		
	Day -1	Day 0	Day 2	Day 7	Day 30
ENROLMENT:					
Eligibility screen	Urine specimen received at microbiology laboratory	Urine culture result reported to physician	Physician treatment decision made	Safety assessment	Safety assessment
Allocation	X				
INTERVENTIONS:					
Reporting		X			
ASSESSMENTS:					
Appropriateness			X		
Adverse Events			X	X	X
Bacteremia			X	X	X
Mortality			X	X	X

Sample size

In the previous trial of the same intervention, modified reporting increased the appropriateness of treatment from 29/55 (52.7%) to 44/55 (80.0%) ($p=0.002$), for an absolute difference of +23%.(11) Accepting a risk of type 1 error of five percent, and a risk of type 2 error of twenty percent, the study will require $2N=90$ patients. To account for missing data, recruitment will be increased to 100 patients.

The microbiology laboratory receives 130 urine specimens per day, with 30 percent reported as significant growth (40 specimens per day). Ten percent are submitted from LTCF (4 positive specimens per day). In the previous trial, approximately 40% of eligible specimens were excluded based on exclusion criteria. Recruitment of 100 specimens will require approximately 40-60 days.

The statistical test to be used is a comparison of proportions between two groups (T test, two-sided analysis). Because true diagnosis may be biased by lack of access to clinical information, an intention to treat analysis including all patients randomized will be performed.

Recruitment

Every urine specimen received for culture during the study period will be assessed for inclusion.

Allocation:

Sequence generation

Randomization sequence will be generated without blocking or stratification (Research Randomizer 4.0)(13).

Allocation concealment

Reporting assignments will be placed into serially numbered, sealed, opaque envelopes.

Implementation

Allocation sequence will be generated by investigators. Investigators will enroll specimens and assign specimens to reporting interventions.

Blinding

Trial participants (physicians) will not be blinded to the intervention because the laboratory report will reveal the intervention. Investigators will be blinded to assignment. Data analyst will not be blinded to assignment.

Data collection methods

After randomization and reporting, a physician investigator will assess inpatients for the true diagnosis of UTI or ASB at two days after reporting. Health records will be accessed including demographics, symptoms, treatment decisions and outcomes.

If patients are discharged from hospital before thirty days, primary care physicians will be contacted by phone for additional clinical information. If patients die before thirty days, available data will be analyzed.

Frequency of physician calls requesting complete reporting will be recorded.

Urine culture is reported according to laboratory protocol by licenced medical laboratory technologists, in categories of significant growth, non-significant growth, and no growth, based on quantity of growth and number of bacterial types detected. Antimicrobial susceptibility is reported according to laboratory protocol, including selected first and second-line antibiotics, as susceptible, intermediate or resistant. Drug cost and dosage suggestion are provided.

Data collection form attached.

Data management

Data collection will use a paper case report form, and entered into a trial database by a graduate student. Variables will be coded appropriately. The dataset will be protected using a

password and stored on a laptop computer during data entry. After data entry is completed, data integrity will be reviewed by a second investigator, and then the dataset will be locked for analysis.

Statistical methods

All specimens randomised and reported will be included in the Intention-to-treat (ITT) analysis. Specimens inappropriately included will be excluded from the Per-protocol (PP) analysis. The proportion of appropriate treatment will be compared using two-sided Pearson chi squared test (SPSS 23.0, IBM, USA). Adjusted analysis may be performed if appropriate. A subgroup defined as specimens in which physicians requested complete reporting will be analysed for appropriateness, compared to the standard reporting arm. Missing data will not be imputed.

Data monitoring

A data monitoring committee will not be used, as a single investigator will assume responsibility for data quality. A single interim analysis at approximately 50% recruitment will be performed, and the study stopped if the primary outcome achieves statistical significance.

Harms

Serious adverse events will be reported to the ethics committee within 24 hours. Adverse events will be collected by the investigators at day 2, day 7 and day 30. Patients with adverse events will be provided care in hospital.

Auditing

There will not be auditing of trial conduct during or after the trial.

Research ethics approval

The protocol will be submitted to the Provincial Health Research Ethics Board.

Physician consent requirement will be requested to be waived because the intervention poses no more than minimal risk to participants. Patient consent requirement will be requested to be waived because physicians were the research subjects. A letter will be sent to all inpatient physicians informing them about the study prior to recruitment, and a debrief meeting, offering an opportunity to withdraw physician participation, will be provided.

The benefit of this study to patients includes a reduction in adverse events caused by inappropriate antibiotic treatment. The risk to patients includes possible untreated UTI. The benefit to physicians includes education toward appropriate treatment of ASB. The risk to physicians includes additional effort to access laboratory results for UTI.

Protocol amendments

Protocol amendments will be submitted to the ethics committee and trial registry and informed to investigators.

Consent or assent

Not applicable.

Confidentiality

Identification of patients will be required during data collection, but will be removed from trial dataset before analysis. No identifiers will be included in reporting of results.

Declaration of interests

The investigators and sponsor hold no financial interests in the trial.

Access to data

The trial dataset and protocol will be accessible to the investigators during the trial, and made publically available after the analysis is completed.

Ancillary and post-trial care

There will be no post-trial care provided.

Dissemination policy

Investigators will communicate trial results via unrestricted publication. All investigators are eligible for authorship, according to contribution.

Biological specimens

There will be no collection, testing or storage of biological specimens for genetic or molecular analysis.

Budget

The only expense of the project will be the graduate student to collect the data, perform the analysis and write the manuscript.

Implications

A reduction in inappropriate antibiotic treatment may reduce complications of treatment such as diarrhea due to *Clostridium difficile*, selection of bacteria towards drug resistance, and cost of treatment. If the intervention is determined to be safe, it may be considered for implementation in routine laboratory practice. The results will generalize to adult inpatients in Canada and around the world.

References

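### The primary outcome cannot detect UTI treated with a drug the isolate resists, an error that withholding susceptibility results could increase

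*Combined protocol and SAP*

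**What the plan says.** The section on participants, interventions and outcomes defines success as follows: "Appropriate therapy is defined as any treatment for UTI, or no treatment for ASB". The failures are the mirror image: "Inappropriate therapy is defined as no treatment for UTI, or treatment for ASB". The Outcomes section adds "Appropriateness is determined by investigators based on chart review, based on diagnosis of UTI or ASB" and "Appropriateness is determined within two days from positive urine culture". Nothing in these sentences asks whether the drug was active against the isolate.

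The arms differ in the information that bears on drug choice. Under Interventions, "The standard report provides bacterial count, bacterial identification and bacterial susceptibility results". In the modified arm, "Physicians receiving modified reports will have the option to call the laboratory to receive complete results, or not"; the report text asks the physician to telephone if UTI is suspected and gives daytime and night contacts.

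The only secondary efficacy outcome is "Proportion of calls from physicians requesting complete report". Statistical methods adds a subgroup of specimens for which the full report was requested, scored by the same definition of appropriateness. Bacteremia and mortality over 30 days and adverse events over seven days are safety outcomes.

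**The concern.** What is randomised is default access to organism and susceptibility results. One error that such a change could increase is treatment of a true UTI with an agent the isolate resists. The primary outcome records that case as appropriate, the same as active treatment. The caller subgroup does not help, because it leaves out physicians who treat without calling, and it uses the same scoring.

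The hypothesis has two parts: less treatment of ASB, and no harm. If inactive treatment were more frequent in the modified arm, the primary difference would overstate that arm's benefit, and no efficacy result would show it. Research ethics approval names untreated UTI as the patient risk, and the outcome does count that against either arm. It does not mention UTI treated with an inactive drug.

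**Working it through.** **Planning figure.** Sample size gives 29/55 (52.7%) against 44/55 (80.0%), two-sided 5% error, 80% power and a total of 90. With p1 = 0.527, p2 = 0.800, mean 0.664 and difference d = 0.273:

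n per arm = [1.96 × √(2 × 0.664 × 0.336) + 0.842 × √(0.527 × 0.473 + 0.800 × 0.200)]² / 0.273² ≈ 46, or 92 in total.

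Unpooled variance gives 88, so the stated 90 is reproduced. It rests on 27.3 points and not on the 23 points printed in the same sentence, which would need 122 to 136. At 50 per arm the power for 27.3 points is 83%.

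**Share of specimens exposed.** Background and rationale reports ASB in 76 of 110 specimens in the earlier trial, so the UTI share is u = 34/110 = 30.9%. In an arm of 50 that is 50 × 0.309 = 15.5 UTIs.

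**Effect of scoring inactive treatment as inappropriate.** Let t be the share of UTIs treated (taken as equal in both arms), and i_mod and i_std the shares of treated UTIs given an inactive drug. Each arm's proportion falls by u × t × i, so the part of the difference that the present definition hides is

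hidden = u × t × (i_mod − i_std).

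For t = 1 and a 10-point excess: 0.309 × 1 × 0.10 = 3.1 points, or 15.5 × 0.10 ≈ 1.5 patients in an arm of 50.

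The documents give no value for t, i_mod, i_std or the call rate. The rows below are assumptions that show the range. Power is for the activity-aware outcome at 50 per arm.

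| t | i_std | i_mod | Hidden (points) | Remaining difference (points) | Power |
|---|---|---|---|---|---|
| 0.8 | 10% | 10% | 0 | 27.3 | 82% |
| 0.8 | 5% | 20% | 3.7 | 23.6 | 69% |
| 1.0 | 10% | 30% | 6.2 | 21.1 | 58% |
| 1.0 | 0% | 40% | 12.4 | 14.9 | 33% |

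To hide the whole effect, the excess of inactive treatment would have to be 27.3 / 30.9 = 88% of all UTIs.

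**Whether the safety outcomes would catch it.** The earlier trial had two bacteremias and two deaths in the modified arm, against one of each in the standard arm, with 55 per arm. With 50 per arm and one event in the standard arm, a two-sided Fisher test needs eight events in the modified arm to fall below 0.05 (1 v 8 gives p = 0.031; 1 v 7 gives p = 0.059).

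**The case against.** A reader might infer that the definition favours the modified arm by construction, or that inactive treatment can arise almost only there. The documents support neither reading.

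- The scoring rule is the same in both arms. It favours the modified arm only if treated UTIs there receive inactive drugs more often.
- The modified report invites a call whenever UTI is suspected, day or night, and full results are released to callers. If physicians who treat UTI call, the bias vanishes.
- Only antibiotic treatment at the time of collection is an exclusion, and the report comes about 24 hours after the specimen is received. Drugs started in between are chosen without this culture's susceptibility results in either arm. Nothing shows that an inactive drug is changed in the standard arm before the two-day assessment. A near-zero standard-arm rate is therefore an assumption, and so is any lower bound above zero for the bias.

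It can also be said that the endpoint measures the decision to treat or not. That fits the hypothesis about ASB and matches the earlier trial, and bacteremia, death and call frequency are recorded.

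All of this stands as a limit on size and certainty, and as a reason to keep the primary definition. It does not close the gap. The plan cannot show that physicians will call, it does not measure what follows when they do not, and the safety events are too few to serve as a substitute.

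**Conclusion.** The gap is plain in the text: drug activity enters neither the primary outcome nor any other efficacy analysis, although the intervention changes default access to susceptibility results. If inactive treatment of UTI differs between arms, the expected direction favours the modified report.

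The size is unknown and may be zero. At the earlier trial's 31% UTI share, the hidden part is up to about 3 points for each 10-point excess of inactive treatment, and 0 to 12.4 points over the assumed values above. That share comes from acute-care inpatients without catheters; this trial enrols long-term care residents, including those with catheters. The blind spot could not plausibly account for the whole 27.3-point planning effect. The point is a cheap improvement that bears mainly on the no-harm conclusion; it does not show that the primary result will be biased.

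**What to change.** Keep the primary definition, which preserves comparability with the earlier trial. Prespecify the following, identically for both arms:

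1. The number and proportion of UTIs treated by day 2 with an agent to which the isolate tests resistant.
2. A sensitivity analysis of the primary outcome in which a treated UTI counts as appropriate only if the isolate tests susceptible to the agent in use at the day-2 assessment.
3. A rule for intermediate and untested agents. This is needed because "Antimicrobial susceptibility is reported according to laboratory protocol, including selected first and second-line antibiotics, as susceptible, intermediate or resistant", so some prescribed drugs may have no result. One option is to report these cases separately and show the analysis with them counted each way.
4. The UTI and ASB components of appropriateness, shown separately by arm.

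The data should be within reach. Full results can be released for modified-arm specimens on request, and Data collection methods already lists treatment decisions among the items taken from health records. The attached data collection form could not be seen, so drug name may or may not already be on it.

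The cost is a small linkage and abstraction burden and one extra analysis. With about 15 UTIs per arm the estimate will be imprecise, so it should be labelled a supportive check.

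### No rule stops a resident from being randomised twice, so one 30-day death or bacteremia can count in both arms; the effect is small and cheap to remove

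*Combined protocol and SAP*

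**What the plan says.** The specimen is the unit at every operative step of the Combined protocol and SAP.

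- Inclusion and exclusion criteria for participants: "Consecutive positive urine cultures collected from patients admitted to LTCF will be included". The four exclusions are a specimen from outside long-term care, pregnancy, "antibiotic treatment at the time of collection", and recent neutropenia. None concerns earlier randomisation.
- Methods: "the specimen will be randomized in the laboratory". Under Implementation, specimens are enrolled and assigned. Under Sequence generation, the list has no blocks or strata, so nothing ties a resident's second specimen to the first arm.
- Recruitment: every specimen received in the study period is assessed.
- Statistical methods: the ITT set is made up of specimens.
- Outcomes: mortality and bacteremia are each measured over thirty days from the positive culture.

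Other sentences count people. Sample size gives the target of 100 in patients and, one paragraph later, in specimens. The same section defines the ITT analysis by patients. The Objectives ask about patients, and about effect "without an increase in bacteremia or death over 30 days".

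The Background says "We propose to repeat the trial using an identical design and intervention" and describes the earlier trial thus: "Results of positive urine cultures from 110 consecutive inpatients at two urban hospitals were randomised".

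**The concern.** Bacteriuria is common in long-term care, and a resident can send more than one specimen in 40-60 days. A resident randomised twice has a 50% chance of being in both arms; with three specimens it is 75%. If that resident dies within thirty days of both cultures, the plan's wording adds the death to each arm. The same holds for bacteremia. A full report on the first culture can also inform the physician who receives a modified report on the second.

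The safety question is part of the research question and depends on very few events. In the earlier trial, "There were two deaths in the modified report group, and one death in the standard report group". With about 50 specimens per arm, one death is about 2 percentage points (1/50).

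The patient and specimen versions of the target and of the ITT set agree only if each resident enters once. The plan's own figures therefore presuppose a rule that it does not contain.

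**Working it through.** **The plan's own figures.** Inputs from Sample size: 29/55 = 0.527 and 44/55 = 0.800, two-sided alpha 0.05, power 80%. The pooled formula is n = [1.96·√(2·p̄·q̄) + 0.842·√(p1q1 + p2q2)]² / (p2 − p1)². With p̄ = 0.664 this is (1.310 + 0.538)² / 0.273² ≈ 46 per arm, or 2N = 92. The unpooled version gives 88. The stated 90 is reproduced, and 90/0.9 = 100. Accrual is 4 × (1 − 0.4) = 2.4 eligible specimens per day, and 100/2.4 = 42 days, which lies within 40-60.

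**Assumptions, because the documents give no repeat rate.** The 100 eligible specimens fall at random on B residents, with equal risk or unequal risk (gamma, shape 1). Allocation is simple 1:1. Pool and period are matched:
- B = 1,000 (assumed), over 42 or 60 days.
- B = 430, the one named facility, at an assumed 430/1,000 of the flow: 2.4 × 0.43 = 1.03 per day, so 100/1.03 = 97 days.

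The Study setting leaves the number of facilities open: "Specimens will be collected from patients admitted to one (or more?) LTCF".

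**Residents in both arms, equal risk.** Expected number = B·[1 − 2(1 − 1/(2B))^100 + (1 − 1/B)^100].
- B = 1,000: 1,000 × (1 − 1.902435 + 0.904792) = 2.4.
- B = 430: 430 × (1 − 1.780333 + 0.792289) = 5.1.

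The chance of no repeat at all is below 1% for B = 1,000 and about 4 in a million for B = 430.

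**Double-counted deaths.** Simulation, 6,000 runs per scenario, uniform culture times, death time exponential after the last culture. Mortality is either 3/110 = 2.7% (the earlier trial, seven days, acute care) or an assumed 30-day 11%. Paired figures are equal / unequal risk.

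| Pool, period | Residents in both arms | Share of deaths counted twice | At least one, 2.7% | At least one, 11% |
|---|---|---|---|---|
| 1,000, 42 days | 2.4 / 4.3 | 1.3-2.6% | 3.4 / 6.2% | 13.6 / 22.6% |
| 1,000, 60 days | 2.4 / 4.3 | 1.1-2.1% | 3.0 / 5.1% | 10.5 / 18.3% |
| 430, 97 days | 5.2 / 8.4 | 1.6-3.0% | 4.0 / 6.4% | 14.3 / 23.5% |

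The expected number counted twice is 0.03-0.07 of 2.2-2.6 deaths at 2.7%, and 0.11-0.26 of 8.9-10.4 at 11%.

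**Sensitivity.**
- If every enrolled culture led to a seven-day course that kept repeats out: 1.7-7.7 residents in both arms, 0.5-1.8% of deaths, and a chance of 1.3-4.0% or 5.8-14.2%.
- If one 430-bed facility met the stated 40-60 days: 2.4-5.9% of deaths, and a chance of 5.8-11.6% or 21.0-40.5%.

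**Direction.** Among simulated trials with a double-counted death and no true effect, the gap in death counts narrowed in 53-68% and widened in 31-43%, compared with counting in the first arm only.

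**Carry-over.** Between 0.9 and 2.9 modified reports follow a standard report on the same resident within 30 days.

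**Primary test.** Each specimen has its own independent allocation, so under the null the arm labels carry no information about outcome, however correlated a resident's outcomes are. In simulation with perfect within-resident correlation, type I error stayed at about 5%.

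**The case against.** The strongest reply is that one entry per resident was intended. The sample size counts patients, and the design is called identical to a trial described as cultures from 110 consecutive inpatients. That is plausible, but none of these sentences is a rule, and the specimen-based text contradicts them. The sentence under Interventions that rules out a change of allocation concerns the single report on one specimen. The antibiotic exclusion blocks re-entry only during a course. The attached data collection form is not in the text available here and may bear on this.

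The specimen is also a defensible unit for efficacy: physicians are the main participants, and each report prompts a separate decision within two days. This stands. It does not carry over to a 30-day death, which belongs to the resident.

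It also stands that the effect is small. In the base scenarios most trials contain no double-counted death. Even with perfect counting, 50 per arm gives chi-squared power of only about 33% to detect a doubling of 11% mortality and about 8% for a doubling of 2.7%.

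A reader might infer three stronger points that are not supported.
- That repeat specimens invalidate the chi-squared test. They break independence between specimens, but type I error holds for the reason shown.
- That the plan is silent on which arm owns a shared event. Read literally, it assigns the event to both.
- That double counting systematically hides harm. In a single trial it can narrow or widen the gap.

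**Conclusion.** The gap is real: as written, a resident can be randomised into both arms, and one 30-day death or bacteremia then counts in each. Nothing elsewhere in the available text closes it. A repeat breaks no stated criterion, so on a natural reading the per-protocol set would keep it too, although inappropriate inclusion is not defined.

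The consequence is minor to moderate and concerns the safety comparison: well under one expected event per trial. The ranges depend on the assumed pool of 1,000, the risk distribution, the accrual share of one facility and the 11% mortality. The 2.7% is a seven-day figure from another setting. The case for acting is that safety depends on a handful of events and that the correction costs little.

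**What to change.** **Minimum.** State that each resident's death or bacteremia is counted once, in the arm of that resident's first randomised specimen, with the thirty days running from that specimen and residents as the safety denominator. This removes the double count at almost no cost. It leaves the carry-over between reports.

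**Preferably also.** Add an exclusion for any resident with a specimen already randomised in this trial, checked against the enrolment log. State the target of 100 and both ITT sentences in residents. The sample size does not change.

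**Cost in recruitment.** The specimens needed for 100 residents are −B·ln(1 − 100/B) under equal risk and 100B/(B − 100) under unequal risk.
- B = 1,000: 105 to 111 specimens, or about 2-5 more days at 2.4 per day.
- B = 430: 114 to 130 specimens, or about 13-29 more days at the assumed 1.03 per day.

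Recurrent cultures would leave the efficacy analysis.

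**A side effect to manage.** About 7-12 of the 100 residents would have a later eligible culture within 30 days; about half, 3.5-6, would be in the modified arm. If those cultures receive full reports, the 30-day safety contrast is diluted, possibly by more than the 1-3 carry-overs that the exclusion removes. The plan should therefore fix before the start which type of report later cultures receive, and record the reports actually issued, by arm. Recording shows the dilution but does not remove it.
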